### **Compensation**

- Participants will receive a \$25 gift card for enrolling in the study and completing the pre-survey.
- Participants will receive a second \$25 gift card for the post-survey.
- Participants will not be compensated for completing the surveys if they received \$25 gift cards for completing the surveys in a prior study cohort.
- Participants will receive a \$40 grocery card per class (5 classes for a total of \$200) to purchase ingredients for the cooking sessions.
- Participants who are repeating a class will not receive a \$40 grocery card if they received one for the same class in a prior study cohort.
- Participants who take part in the interviews will receive an additional \$25 gift card.
- Participants who are absent for a session will not receive a \$40 grocery card for the following session until they confirm with a staff member that they plan to attend the following session.
- Participants who are absent for 2 or more consecutive sessions will not receive a \$40 grocery card until they attend another session.

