## Study Population

- It is anticipated that program participants will be low-resource and ethnically diverse, reflective of UT Physicians patients at the clinics serving the Acres Homes neighborhood of Houston.
- Inclusion Criteria:
  - Receiving care at UT Physicians clinics;
  - Adult patients (18 to 75 years) diagnosed with type 2 diabetes and elevated body mass index ( $\geq 25$ );
  - HbA1c labs and clinic-assessed weight completed within the last 3 months;
  - English speaking or Spanish speaking.
  - Can obtain groceries before each class (intervention group only)
- Exclusion Criteria:
  - Patients without the technological support needed to participate (e.g., reliable internet and device - cell phone, tablet or laptop);
  - Patients with an uncontrolled impairment that interferes with ability to participate.
- Recruitment: Patients meeting the aforementioned inclusion criteria will be invited to participate. We will conduct separate recruitment for intervention and control participants- with the intervention participants recruited from the Victory and Greens UT Physicians clinics that serve Acres Homes, and control participants recruited from the Jensen UT Physicians clinic. Jensen has a similar patient population to Victory and Greens, and is relatively close geographically, while still sitting outside of the target neighborhood of Acres Homes. UT Physicians' care coordinators will assess patient eligibility to participate in the program and share either a flyer or an interest form link with eligible patients. Patients will complete the interest form giving UTHHealth their contact information. UTHHealth staff will reach out to patients and explain the program (time commitment, class days/time). If patient is interested, UTHHealth study staff will perform a technology screening since all classes will be held virtually. After screening, UTHHealth will send an online informed consent and pre-survey.

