### **Statistics**

- 132 participants are planned to be enrolled, 66 from intervention clinics and 66 from control clinics.
- All participants that enroll in the program will be included in the analysis. Saturation point is considered attendance of 4 out of 5 sessions (80%).
- Statistical analysis will include descriptive and frequency analysis of responses, a pre-post analysis using paired t-test, chi-square test, and Analysis of Covariance to determine changes in biometric and behavioral measures pre to post NCCM program participation.
- Level of significance will be set at  $p < 0.05$ .
- Qualitative data will be analyzed for themes using standard methods and NVivo software. Responses will be summarized, and a report will be created to provide information to our research investigators and the public health community.

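### Returning participants are foreseen and not excluded, so a baseline can follow exposure to the classes, and no rule limits each person to one record.

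*Combined protocol and SAP*

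**What the plan says.** Compensation has two rules for people who come back. On surveys, it says "Participants will not be compensated for completing the surveys if they received" the gift cards "for completing the surveys in a prior study cohort". On classes, it says "Participants who are repeating a class will not receive" a grocery card "if they received one for the same class in a prior study cohort". Loss of payment is the only consequence stated.

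Study Population says "Patients meeting the aforementioned inclusion criteria will be invited to participate". There are two exclusion criteria. One begins "Patients without the technological support needed to participate" and the other concerns an uncontrolled impairment. Neither mentions earlier participation.

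Statistics says "132 participants are planned to be enrolled, 66 from intervention clinics and 66 from control clinics", and then "All participants that enroll in the program will be included in the analysis". The planned methods are the paired t-test, the chi-square test and ANCOVA, with no term for repeated entry.

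Study Procedures places the pre-survey ahead of the first class and ties the baseline EMR values to a 90-day window around the start of the programme. It does not say which start applies to someone who has started before. Data handling and record keeping gives each participant a unique study number and links EMR to survey data by name, date of birth and zip code. It sets no rule for the analysis of returning people.

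**The concern.** Read together, the eligibility, payment and analysis-set rules admit people whose baseline is not a baseline. Someone who has already taken the classes may arrive with changed diet, cooking skills and HbA1c. The change from that point measures a second pass through the programme, and it would be averaged with first-pass changes as if the two were the same quantity.

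A second issue arises only if the earlier cohort belonged to this study. One person could then hold two records, and the planned tests would treat them as two people. The 66 could also be reached with fewer than 66 individuals. The Publication Plan intends the results as preliminary data for a full-scale trial, so a diluted effect or an inflated count would carry into that trial's design.

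**Working it through.** **The plan's own figure.** 66 + 66 = 132, as stated. The documents give no effect size, standard deviation, power or dropout, so there is no sample-size calculation to reproduce. No stated number is contradicted; what is missing is a rule.

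**Can the situation arise?** Repeat surveys and repeat classes are each addressed in Compensation, no exclusion stops them, and everyone who enrols is analysed. Study Procedures uses the word cohort for this study's own English and Spanish class groups, which favours the within-study reading. Five sessions span 4 intervals of one or two weeks, or 4 to 8 weeks, so several cohorts fit in a one-year study. EMR follow-up is allowed up to 90 days after completion in Study Procedures and up to 6 months in Data handling. One HbA1c could thus be the follow-up value for a first enrolment and the baseline for a second.

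**Dilution.** Let r be the share of intervention records that are repeats and f the second-pass effect as a fraction of the first. The averaged effect is (1 − r) + r·f = 1 − r(1 − f) of the first-pass effect, so the loss is r(1 − f). Neither r nor f is in the documents. I assume r from 0 to 20% and f from 0 to 1.
- r = 0, or f = 1: loss 0%.
- r = 0.05, f = 0.5: loss 0.05 × 0.5 = 2.5%.
- r = 0.20, f = 0: loss 20%.

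If repeats are counted as records, distinct people = 66(1 − r), which runs from 66 down to 66 × 0.80 = 52.8, about 53.

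**Power, for illustration only.** I assume a two-sided 5% test (sidedness is not stated) and the standardised difference that 66 per arm detects with 80% power: (1.960 + 0.842) × √(2/66) = 0.488. With m repeats among the 66 intervention records, the difference is multiplied by 1 − (m/66)(1 − f). The last column keeps one first-enrolment record per person and does not replace the repeats.

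| m of 66 | Distinct people | Effect kept, f = 0 | Effect kept, f = 0.5 | Power, f = 0 | Power, f = 0.5 | Power, one record each |
|---|---|---|---|---|---|---|
| 0 | 66 | 100% | 100% | 80% | 80% | 80% |
| 3 | 63 | 95.5% | 97.7% | 76% | 78% | 79% |
| 7 | 59 | 89.4% | 94.7% | 71% | 76% | 78% |
| 13 | 53 | 80.3% | 90.2% | 61% | 71% | 75% |

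At f = 1 the effect is not diluted. Enrolling 66 distinct people restores 80%.

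**Type I error if duplicates are treated as independent.** With m pairs and within-person correlation ρ, the variance of the intervention mean is multiplied by 1 + 2mρ/66. The true standard error exceeds the nominal one by the factor √[(1 + 2mρ/66 + 1)/2].
- m = 3, ρ = 0.3: variance factor 1.027, type I error about 5.2%.
- m = 13, ρ = 0.8: variance factor 1.315, type I error about 6.9%.

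Both m and ρ are assumed. If change scores are analysed and one HbA1c ends the first record and begins the second, ρ could be negative and this inflation would not occur.

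**The case against.** The strongest reply is that double entry is nowhere stated. Statistics counts participants, not records, and each participant has one unique study number, so the natural reading may be one person, one entry. The earlier cohort may also belong to a related study, in which case the person enters this data set once. The payment clauses are conditional limits and say nothing about analysis, and the class clause could refer to one repeated session. This stands to the extent that a reader who infers that people will be counted twice goes beyond the text. It does not dispose of the point. The study number makes repeats detectable but does not say which enrolment supplies the baseline. If the earlier cohort was in a related study, the baseline still follows exposure.

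Two further inferences are tempting and not supported. One is that the programme effect is certainly biased towards zero. With no repeats, or a second pass as effective as the first (for example in someone who attended little the first time), there is no dilution, so the range must start at 0%. The other is that only the intervention arm is affected. The survey-payment rule is not limited by arm and both arms complete surveys, so controls may also be repeat respondents, although this protocol gives them no classes.

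It is also fair to say that this is a pilot with no stated power target, so the power figures only give a sense of scale.

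**Conclusion.** The concern holds in a limited form. Followed as written, the plan admits people whose pre-survey and baseline HbA1c come after exposure to the same curriculum. This does not depend on which study the earlier cohort belonged to. Two records from one person are permitted but not shown: that needs the earlier cohort to be part of this study and the unique code not to be used to merge entries.

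The size is unknown because no repeat rate is given. Under the assumed ranges, dilution of the programme effect is 0-20%, and 66 records would be about 53-66 people if repeats count as records. The upper end needs about 13 of 66 records to be repeats with no further benefit. This should be settled before analysis, since the remedy is cheap and the choice should not be made after the results are seen.

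**What to change.** Add to Statistics, and qualify the sentence on including all who enrol to match:

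> Each person contributes one record, from their first enrolment, with baseline survey and EMR values taken before any NCCM class. Repeat enrolments are not analysed as new records and do not count towards the 66. People exposed to NCCM classes before this study are left out of the primary analysis (or included only in a sensitivity analysis), and the number of repeaters is reported by arm.

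Keep EMR follow-up timed from programme completion, as Study Procedures and Data handling and record keeping both do. Timing it from first enrolment would conflict with them. Say in Compensation whether a prior cohort means an earlier cohort of this study, of a related study, or either.

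No new exclusion criterion is needed, which matters because this version is dated 04/08/2024, inside the stated October 2023 to September 2024 study period. An analysis rule can be applied to people already enrolled, and repeaters may still attend classes.

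The cost is a short paragraph and a duplicate check on name and date of birth, which the linkage already uses. Staff must already know who received cards in a prior cohort to apply the payment rules. The downside is that a few returning people no longer count towards the 66. Without replacement, the illustrated power is 75-79% for 13 down to 3 repeats, against 61-76% if the repeats stay in and show no further change.

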### **Statistics**

- 132 participants are planned to be enrolled, 66 from intervention clinics and 66 from control clinics.
- All participants that enroll in the program will be included in the analysis. Saturation point is considered attendance of 4 out of 5 sessions (80%).
- Statistical analysis will include descriptive and frequency analysis of responses, a pre-post analysis using paired t-test, chi-square test, and Analysis of Covariance to determine changes in biometric and behavioral measures pre to post NCCM program participation.
- Level of significance will be set at  $p < 0.05$ .
- Qualitative data will be analyzed for themes using standard methods and NVivo software. Responses will be summarized, and a report will be created to provide information to our research investigators and the public health community.

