## Objectives

- The purpose of this study is to implement a five-session hands-on virtual CM program (to be held weekly or bi-weekly) among patients with diabetes and elevated body mass index receiving care UT Physicians clinics serving the Acres Homes neighborhood, and comparing their outcomes to patients in usual care from UT Physicians clinics outside of the Acres Homes service area.
- The overall goals of this project are to:
  - To implement adapted virtual CM curriculum among target population
  - To assess if program participation improves participant dietary behaviors, nutrition knowledge, and cooking skills and behaviors above standard of care.
  - To assess if program participation improves patient levels of HbA1c, Body Mass Index, Blood Pressure, HDL, LDL and Triglycerides above standard of care.
  - To assess if social determinants of health modify the association between participating in the program and any of the aforementioned outcomes.
  - To determine the feasibility and reproducibility of virtual synchronous CM classes.

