## Study Design

- This study is a pilot study with a quasi-experimental design using assigned intervention and control clinics.
- Study participants will be evaluated prior to and immediately after the program via pre and post survey.
- EMR data will be reviewed at baseline and completion of program
- This one-year project will include:
  - a) conducting the virtual CM program for approximately 66 intervention patients with diabetes receiving care at UT Physician Clinics serving the Acres Homes neighborhood in Houston
  - b) conducting program evaluation (pre- and post-test surveys and EMR data) using data from those 66 intervention participants and 66 control participants recruited from UT Physicians clinics outside of the Acres Homes service area
- The pre-post survey will evaluate participants’ dietary behaviors, nutrition knowledge, cooking skills and behaviors along with demographic information. The EMR data will evaluate improvements in clinical data: HbA1c, Body Mass Index, Blood Pressure, HDL, LDL and Triglycerides. The results will be used to determine if virtual CM education can be effective in improving certain health outcomes, dietary behaviors and cooking-related constructs.
- There are a few minimal risks known to taking part in this study. Knives will be utilized raising the risk for minor cuts. Stove tops, ovens, microwaves, and other kitchen equipment will be utilized raising the risk for minor burns. Food items containing known allergens will be utilized raising the risk for allergic reaction. We anticipate participation in this study to be of minimal risk and do not expect our program or surveys to cause emotional distress.

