- The virtual curriculum will include five 90-minute sessions (to be held weekly or bi-weekly). Participants will also be expected to shop for groceries ahead of the sessions to participate in the program. A gift card will be provided for groceries (\$40 per class = \$200 total).
- Partnership with UT Physicians sites will allow use of Electronic Medical Record (EMR) data: patient level data for HbA1c, Body Mass Index, Blood Pressure, HDL, LDL and Triglycerides collected as part of their regular standard of care and documented within the EMR. No additional visits, screenings or time will be necessary for participation in the program. Data will be abstracted and shared by clinic site to UTHealth at: baseline (within 90 days of starting the NCCM program) and at program completion (within 90 days of NCCM program completion).
- Informed consent will be obtained electronically via REDcap prior to survey administration. Participants will review the consent documents. Participants will be allowed to contact the Study Coordinator with any questions prior to completing the consent form or the survey. Participants will be allowed to leave the project at any time.
- Participants will be asked to complete an electronic 15-minute survey via REDcap at two timepoints: pre-test survey before the first class and a post-test after the conclusion of the program. The electronic pre- and post-test surveys will collect information on 1) dietary intake, 2) cooking skills, 3) cooking-related psychosocial constructs, 4) diabetes management, and 5) demographics (age, sex, race/ethnicity, education, employment status, preferred language spoken at home, and participation in government assistance programs will be collected at baseline at the start of the program). Survey items are described in detail in the measurement resource table below.

Primary Outcome- measured at both pre-survey (baseline) and post-intervention (follow-up)		
HbA1c	Measured by the clinic at baseline and follow-up	
Secondary Outcomes- measured at both pre-survey (baseline) and post-intervention (follow-up)		
Other clinical measures	Body Mass Index (height and weight), Blood Pressure, HDL, LDL and Triglycerides measured by the clinic at baseline and follow-up	
Variable (Construct)	Number of items and sample question	Source citation

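### The Statistics section never names the arm comparison as the deciding test, so a within-arm HbA1c change could be reported as a programme benefit

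*Combined protocol and SAP*

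**What the plan says.** The question is posed between arms. The Objectives section gives the purpose as running the programme and "comparing their outcomes to patients in usual care from UT Physicians clinics outside of the Acres Homes service area". It asks whether participation "improves patient levels of HbA1c, Body Mass Index, Blood Pressure, HDL, LDL and Triglycerides above standard of care", and asks the same of the dietary, knowledge and cooking outcomes. Study Design describes a "quasi-experimental design using assigned intervention and control clinics" and says the evaluation uses data from 66 intervention and 66 control participants. The outcome table in Study Procedures makes HbA1c the single primary outcome, "Measured by the clinic at baseline and follow-up".

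The Statistics section repeats the 66 and 66 and sets one significance level, p < 0.05, for everything. It describes the quantitative analysis in one sentence: "a pre-post analysis using paired t-test, chi-square test, and Analysis of Covariance to determine changes in biometric and behavioral measures pre to post" programme participation. It does not say which test decides the HbA1c question, what the ANCOVA's factor and covariates are, or what the chi-square test compares. The analysis set is described as "All participants that enroll in the program will be included in the analysis".

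The Objectives also include a goal on effect modification, "To assess if social determinants of health modify the association between participating in the program and any of the aforementioned outcomes". No analysis in the Statistics section corresponds to it.

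**The concern.** A paired test in the intervention arm asks whether HbA1c changed. It does not ask whether HbA1c changed more than it would have under usual care. The observed change combines any programme effect with ongoing diabetes care, secular trend and regression to the mean. The controls are recruited to separate these, and a paired test on one arm discards them.

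Running the paired test in each arm and contrasting the two p-values does not repair this. A significant result in one arm and a non-significant one in the other can easily arise when both arms changed equally.

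With several tests listed, none ranked first and all described as pre-to-post, an author could report a significant within-arm change as the finding without departing from the plan. Study Design says the results will be used to judge whether the programme can be effective, and the Publication Plan says they will inform a full-scale trial. An effect estimate that is partly usual-care drift would carry into that trial's design.

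**Working it through.** **Inputs from the documents.** 66 patients per arm (66 + 66 = 132, as stated) and a significance level of 0.05. The documents give no effect size, SD, power or dropout, so no planned power figure can be reproduced. Sidedness is not stated; two-sided is assumed.

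**Assumed inputs.** HbA1c improvement under usual care alone (drift): 0.3 points, range 0.1 to 0.4. SD of individual change: 1.2 points, range 1.0 to 1.5. For the ANCOVA: SD of HbA1c 1.6 and pre-post correlation 0.6. These two values imply an SD of change of 1.6 × √(2 − 2 × 0.6) = 1.6 × √0.8 = 1.43, so the paired test is shown at 1.43 as well as at 1.2. All 66 patients are taken to have both measurements.

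**Step 1. Paired t-test in the intervention arm, zero programme effect.** The statistic is noncentral t with 65 degrees of freedom and noncentrality (drift / SD of change) × √66. The two-sided critical value is 1.997.

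| Drift | SD of change | Noncentrality | P(p < 0.05) |
|---|---|---|---|
| 0.3 | 1.2 | 0.25 × 8.124 = 2.03 | 52% |
| 0.3 | 1.43 | 0.210 × 8.124 = 1.70 | 39% |
| 0.1 | 1.5 | 0.067 × 8.124 = 0.54 | 8% (lowest) |
| 0.4 | 1.0 | 0.40 × 8.124 = 3.25 | 89% (highest) |

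**Step 2. Contrasting the two within-arm p-values.** If both arms have the same true change and each paired test is significant with probability P, the pattern of significant in intervention but not in control has probability P(1 − P). At P = 0.52 this is 0.52 × 0.48 = 0.25, which is also the ceiling of the expression. It is lower for P away from one half.

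**Step 3. Between-arm ANCOVA under the same conditions.** A simulation used 4,000 trials per setting, 66 per arm, correlation 0.6, comparable arms and no arm effect. The common change ran from 0 to 0.5 SD of change. The arm term was significant in 4.5% to 5.7% of trials. Over 0.2 to 0.5 SD, the paired test in the intervention arm was significant in 36% to 98%.

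**Step 4. Precision of the arm contrast.** SE = SD × √(1 − r²) × √(2/n) = 1.6 × 0.8 × √(2/66) = 0.223 points. The 95% CI is about ± 1.96 × 0.223 = ± 0.44 points.

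**Step 5. What the arm contrast does not remove.** Study Population names two intervention clinics and one control clinic. Suppose the arms differ by a stable 0.5 points and neither changes (again an assumption). With correlation 0.6 the ANCOVA arm term is biased by (1 − 0.6) × 0.5 = 0.2 points. At SE 0.223 it rejects about 15% of the time. The 5% in Step 3 therefore holds for drift common to comparable arms, and not for arms that differ.

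**The case against.** The strongest reply is that ANCOVA is in the plan. It normally needs a grouping factor, and arm is the obvious one in this design. The Objectives state a comparison with usual-care patients, and Study Design places the 66 controls in the evaluation data. This stands. A reader might infer that the trial plans to judge success by paired tests, or has no between-arm analysis. The documents do not support either reading; the arm comparison is left unspecified and unranked.

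A reader might also infer from "All participants that enroll in the program will be included in the analysis" that controls are excluded from analysis. The preceding bullet enrols 66 patients from control clinics, and Study Design uses their data, so this is loose wording only.

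The reply is also right that the drift has no source in the documents and that the rejection rate depends heavily on it and on the SD. The figures show that the risk can be large; they do not predict its size in this trial.

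The last reply is that this is a pilot. That argues for modest claims. It does not justify leaving the deciding test open, because the pilot sets its own goals of improvement relative to usual care.

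What remains is that no other section supplies the arm term, the covariates, the order of tests or the effect-modification analysis. One of the tests listed cannot answer the stated question.

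**Conclusion.** The concern holds as a mismatch between a between-arm objective and an analysis described only as pre-to-post. An arm comparison was probably meant, but the plan does not commit to it, and a significant within-arm change could be reported as a programme benefit.

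Under the central assumption of 0.3 points of drift, that would happen with no programme effect in about 39% to 52% of trials, depending on whether the SD of change is 1.43 or 1.2. The wide range of 8% to 89% reflects how little the documents fix. The qualitative conclusion does not depend on these values: any drift shared by both arms raises the paired test's rate above 5%, whereas the arm contrast holds about 5% when the arms are comparable.

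It would go too far to infer that an ANCOVA with an arm term would make the result confirmatory. Allocation is by clinic and not randomised, so the adjusted difference removes shared drift but cannot be separated from differences between clinics.

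**What to change.** In the Statistics section, replace the sentence on quantitative analysis with text to this effect:

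- The primary analysis is an ANCOVA of follow-up HbA1c on arm (intervention versus control), adjusted for baseline HbA1c and a short, pre-specified set of the baseline covariates already collected, in enrolled participants of both arms. The adjusted arm difference, with its 95% CI and a two-sided 0.05 test, is the primary result.
- The same model is used for the other continuous outcomes, reported as estimates with CIs.
- Within-arm pre-post changes are reported descriptively, without p-values.
- Modification by social determinants is assessed by arm-by-determinant interaction terms, labelled exploratory.
- Allocation is by clinic and not randomised, with two intervention clinics and one control clinic. The arm difference removes drift common to both arms but cannot be separated from clinic differences. It is preliminary, not confirmatory.

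As a clarification only, describe the analysis set as those enrolled in the study, in either arm.

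The cost is drafting, plus choosing the covariates before outcome data are examined. No new data are needed. The headline p-value may be less favourable than a within-arm test would give: at 80% power the detectable effect is 0.345 SD of change for the paired test and 0.488 SD for an unadjusted between-arm comparison of change. For SDs of 1.0 to 1.5 points, these are 0.34 to 0.52 and 0.49 to 0.73 points. Follow-up HbA1c comes from routine care without added visits, so the handling of missing values needs its own rule, which this wording does not supply.
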